## PROTOCOL AMENDMENT SUMMARY OF CHANGES

### DOCUMENT HISTORY

Document	Country/countries impacted by amendment	Date
Protocol Version 3	All, including Canada	11 July 2019
Protocol Version 2.1 (from Version 1.1)	Canada	02 March 2018
Protocol Version 1.1 (from Version 1)	Canada	06 July 2017
Protocol Version 2	All	09 February 2018
Protocol Version 1	All	19 January 2017

### Present amendment to the protocol (11-July-2019)

This is a global amendment to the protocol V2.0 and V2.1, and includes specific requirements for Canada in Appendix B.

### OVERALL RATIONALE FOR THE AMENDMENT

The primary reason for this amendment to Protocol 997HA402 is to reduce the number of subjects to be enrolled, to clarify the timing for subjects moving from interim ITI visits to ITI outcome assessment visits, and to clarify sample collection schedules for ADA. Additional updates have been made for Canada and these country-specific changes are outlined in Appendix B.

### PROTOCOL AMENDMENT SUMMARY OF CHANGES

Section # and Name	Description of Change	Brief Rationale
Synopsis, Section 7.1, and Section 16.1.	Following texts or similar texts have been added in the sections:  This study will enroll up to 17 subjects, Or Approximately, 17 subjects will be treated	The primary reason for this amendment to Protocol 997HA402 is to reduce the number of subjects to be enrolled, to clarify the timing for subjects moving from interim ITI visits to ITI outcome assessment visits, and to clarify sample collection schedules for ADA, and to incorporate requests by Health Canada.
Section 4.2, Section 7.2.2, Section 7.2.2.2, and Section 13.1.2.1	Clarification for the timing for subjects moving from interim ITI visits to ITI outcome assessment visits was added to the sections and Table 1, Table 1 footnote 13, Table 2 footnote 11, and Figure 2 were updated.	
Section 4.2 and Section 13.5.2	ADA sample collection has been clarified in Table 1, footnote 10.	
Section 4.2, Section 8.1, Section 13.5.4, Section 14.2, Section 15.4.1, Section 15.5.1, and Appendix B	Specific changes for Canada from Protocol 1.1 and 2.1	

Two new appendix sections have also been created to display history of protocol amendments (Appendix A) and country specific requirements (Appendix B).

CONFIDENTIAL

The information contained herein may not be used, disclosed, or published without the written consent of  
Bioverativ Therapeutics Inc.

Page 10

## 2. LIST OF ABBREVIATIONS

ADA	anti-drug antibody
AE	adverse event
aPCC	activated prothrombin complex concentrate
aPTT	activated partial thromboplastin time
BU	Bethesda Unit
CD4	cluster of differentiation 4
CHO	Chinese hamster ovary
CRO	contract research organization
DHA	Directions for Handling and Administration
ED	exposure day
EDC	electronic data capture
EHL	extended half-life
EOT	end of treatment
EPD	electronic patient diary
FEIBA	factor eight inhibiting bypassing activity
FVIII	coagulation factor VIII
GCP	Good Clinical Practice
HBV	hepatitis B virus
HCV	hepatitis C virus
HIV	human immunodeficiency virus
HLA	human leukocyte antigen
ICF	informed consent form
ICH	International Council for Harmonisation
IITR	International ITI Registry
IQR	interquartile range
IR	incremental recovery
ITI	immune tolerance induction
ITIFAS	ITI full analysis set
IU	international units
IV	Intravenous
IXRS	Interactive Web Response System
NAITR	North American ITI Registry
NGNA	N-glycolylneuraminic acid
pdFVIII	plasma-derived FVIII
PK	pharmacokinetics
rFVIIa	recombinant activated factor VII
rFVIII	recombinant coagulation factor VIII
rFVIIIFc	recombinant coagulation factor VIII Fc fusion protein
SAE	serious adverse event
SAP	Statistical Analysis Plan

CONFIDENTIAL

The information contained herein may not be used, disclosed, or published without the written consent of  
Bioverativ Therapeutics Inc.

Page 12

SUSAR	suspected unexpected serious adverse reaction
$t_{1/2}$	half-life
TPFAS	Tapering Period full analysis set
ULN	upper limit of normal
USA	United States of America
VWF	von Willebrand factor

CONFIDENTIAL

The information contained herein may not be used, disclosed, or published without the written consent of  
Bioverativ Therapeutics Inc.

Page 13

VV-CLIN-0542000 3.0

### 3. SYNOPSIS

Tracking Number:	997HA402
Protocol Title:	A Non-Controlled, Open-Label, Multicenter, Study of Efficacy of rFVIIIFc for Immune Tolerance Induction (ITI) in Severe Hemophilia A Subjects with Inhibitors Undergoing the First ITI Treatment
Version Number:	2.0
Name of Study Treatment:	Antihemophilic factor VIII (recombinant) Fc fusion protein; rFVIIIFc; Eloctate®; Elocta®
Study Indication:	Hemophilia A, ITI
Phase of Development:	4
Rationale for the Study:	
Hemophilia A (coagulation factor VIII [FVIII] deficiency) is a rare X-linked bleeding disorder and the most common type of hemophilia. The most serious treatment complication for patients with hemophilia A is the development of inhibitory immunoglobulin antibodies to FVIII. Inhibitors result in rapid clearance of infused FVIII and marked reduction, or absence, of efficacy of FVIII treatment. FVIII-bypassing agents such as activated prothrombin complex concentrate (aPCC [FEIBA]) or recombinant activated factor VII (rFVIIa [NovoSeven]) are used to treat acute bleeding in patients with high-titer inhibitors, but inhibitor eradication remains the goal of long-term management.
 
Immune tolerance induction (ITI) therapy using frequent administration of high doses of FVIII is the only proven strategy shown to achieve antigen-specific tolerance (Kempton et al., 2014; Valentino et al., 2015). ITI usually attempts to eliminate high-responding FVIII inhibitors (<math>\geq 5</math> Bethesda Unit [BU] titer). ITI regimens employ different doses and dosing frequencies of FVIII, and they may or may not involve adjunctive immunomodulatory therapy (Franchini et al., 2011; Valentino et al., 2015). Currently, a range of FVIII products and dosing regimens are used for ITI because there is no clear consensus on an optimal regimen (Franchini et al., 2011).

CONFIDENTIAL

The information contained herein may not be used, disclosed, or published without the written consent of Bioverativ Therapeutics Inc.

Page 14

VV-CLIN-0542000 3.0

In the International ITI Study, a prospective randomized study comparing a high-dose (200 international units [IU]/kg/day) and a low-dose (50 IU/kg 3 times per week) FVIII regimen, subjects in the high-dose arm achieved a negative titer (median 4.6 months [interquartile range (IQR) 2.8 to 13.8] vs. 9.2 months [IQR 4.9 to 17.0];  $p = 0.017$ ) and a normal recovery (median 6.9 months [IQR 3.5 to 12.0] vs. 13.6 months [IQR 8.7 to 19.0];  $p = 0.001$ ) significantly more rapidly than subjects in the low-dose arm. High-dose subjects also experienced significantly fewer bleeding episodes than low-dose subjects, and for this reason, the data safety monitoring board recommended study termination ([Hay & DiMichele, 2012](#)).

These findings and limited experience in patients with hemophilia who have inhibitors have led to an interest in investigating the use of the Extended Half-Life (EHL) recombinant coagulation factor VIII Fc fusion protein (rFVIIIFc) in ITI. rFVIIIFc was approved in the United States of America (USA), Canada, and Japan in 2014 with the name of Eloctate and in Europe in 2015 with the name of Elocta.

#### Study Objectives and Endpoints:

#### Objectives

The primary objective of the study is to describe the time to tolerization (ITI success, i.e., inhibitor titer  $<0.6$  BU/mL, rFVIIIFc incremental recovery [IR]  $\geq 66\%$  of the expected IR, and  $t_{1/2} \geq 7$  hours) with rFVIIIFc in subjects within a maximum of 12 months (48 weeks) of ITI treatment.

The secondary objectives are as follows:

- To describe the outcome of ITI treatment
- To describe the relapse rate over the 48-week (12-month) period following successful ITI performed with rFVIIIFc
- To describe the intercurrent bleeding during the ITI Period and during the 48-week (12-month) period after successful ITI performed with rFVIIIFc
- To describe the safety and tolerability of rFVIIIFc when used for ITI
- To evaluate the impact of ITI treatment with rFVIIIFc on health economics and adherence

CONFIDENTIAL

The information contained herein may not be used, disclosed, or published without the written consent of Bioverativ Therapeutics Inc.

Page 15

The exploratory objectives are as follows:

- [REDACTED]
- [REDACTED]
- [REDACTED]

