The study consists of 1) a 4-week (1-month) Screening Period; 2) a maximum of a 48-week (12-month) ITI Period; 3) a minimum of a 16-week (4-month) Tapering Period after all criteria for tolerization have been met; and 4) a 32-week (8-month) Follow-Up Period. Only subjects who achieve ITI success will enter the Tapering and Follow-Up Periods. During the Tapering and Follow-Up Periods, the subject's dose will be adjusted to achieve the prophylactic dose.

Study Location and Number of Sites:

Approximately 30 sites in the USA, Europe, Japan, and Canada

Number of Planned Subjects:

Up to 17 subjects

Study Population:

This study will be conducted in male subjects of any age with severe hemophilia A and high-titer inhibitors (historical peak  $\geq 5$  BU/mL), who have been previously treated with any plasma-derived FVIII or recombinant conventional or EHL FVIII and are undergoing ITI treatment for the first time.

CONFIDENTIAL

The information contained herein may not be used, disclosed, or published without the written consent of Bioverativ Therapeutics Inc.

Page 17

VV-CLIN-0542000 3.0

Detailed criteria are described in Section 8.

Treatment Groups: This is a single-arm study that will enroll up to 17 subjects

Duration of Treatment and Follow-Up: Study duration for each subject will vary based on time to ITI success. The maximum individual subject study duration is expected to be approximately 2 years.

CONFIDENTIAL

The information contained herein may not be used, disclosed, or published without the written consent of Bioverativ Therapeutics Inc.

[figure not shown]
Page 18

VV-CLIN-0542000 3.0

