### 5.1. Overview of Immune Tolerance Induction in the Clinical Management of Hemophilia A

Hemophilia A is a rare X-linked bleeding disorder that is caused by a functional deficiency of FVIII, a cofactor in the intrinsic coagulation pathway. Hemophilia A is the most common type of hemophilia and is categorized based on endogenous FVIII activity levels as severe ( $<1$  international units [IU]/dL), moderate (1 to 5 IU/dL), and mild ( $>5$  to  $<40$  IU/dL) ([ISTH Factor VIII/IX Scientific Subcommittee \(SSC\) Working Party on Definitions in Hemophilia, 2011](#); [Srivastava et al., 2012](#); [White et al., 2001](#)). As there is no available cure for hemophilia A, current treatment focuses on replacement therapy with clotting factor concentrates, namely plasma-derived FVIII (pdFVIII) or recombinant factor VIII (rFVIII) products.

The formation of neutralizing anti-FVIII alloantibodies (inhibitors) represents the most serious complication related to hemophilia treatment ([Kempton et al., 2014](#)). Inhibitors are immunoglobulin G antibodies formed against specific epitopes of the FVIII molecule, which can neutralize the coagulation activity of FVIII in plasma and reduce the recovery and half-life ( $t_{1/2}$ ) of FVIII. Inhibitors result in rapid clearance of infused FVIII and marked reduction, or absence, of efficacy of FVIII treatment. Approximately 30% of previously untreated patients with severe hemophilia A develop inhibitors following exposure to replacement FVIII ([Franchini et al., 2013](#); [Gouw et al., 2013](#)). The presence of an inhibitor makes it more difficult to control bleeding because patients no longer respond to standard doses of replacement FVIII. As a result, patients with inhibitors are prone to more bleeds, which can lead to severe joint disease and physical disability and, consequently, reduced quality of life ([Scalone et al., 2006](#)). Patients with inhibitors also have a higher risk of mortality due to bleeding complications ([Walsh et al., 2015](#)).

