## **16. STATISTICAL METHODS AND DETERMINATION OF SAMPLE SIZE**

The objectives of the study and the endpoints to be analyzed are listed in Section 6.

Detailed methodology for summary and statistical analyses of the data collected in this study will be documented in a Statistical Analysis Plan (SAP). In general, continuous variables will be summarized by descriptive statistics, which includes the number, mean, median, standard deviation, minimum, and maximum. Categorical variables and response variables will be presented with the number and percentage in each category. Unless otherwise indicated, analysis will be performed separately for the ITI, Tapering, and Follow-Up Periods. No formal statistical hypothesis testing using inferential statistics will be performed.

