### **16.1. Sample Size Considerations**

Because the number of subjects who have severe hemophilia A and developed inhibitors is small, the determination of sample size for this study is constrained by the availability of subjects. To describe the duration of time needed to develop tolerization from the onset of ITI, the study plans to prospectively enroll up to 17 subjects who are to receive ITI for the first time.

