#### Number of bleeding episodes during ITI, Tapering, and Follow-Up Periods

The number of bleeding episodes during ITI will be summarized by month using the ITIFAS. Descriptive statistics for annualized bleeding rate over both Tapering and Follow-Up Periods will also be summarized using the TPFAS. The rate for each subject will be annualized to account for potential difference in Tapering and Follow-Up Periods.

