#### Number of hospitalization days

Number of hospitalization days will be summarized descriptively for the ITI Period using the ITIFAS and for the combined Tapering and Follow-Up Periods using the TPFAS.

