2 SAMPLE SIZE DETERMINATION

Because the number of patients who have severe hemophilia A and have developed inhibitors is small, the determination of sample size for this study is constrained by the availability of patients. To describe the duration of time needed to develop tolerization from the onset of ITI, the study plans to prospectively enroll up to 30 patients who are to receive ITI for the first time.

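### Days away and hospitalization days have no pre-ITI history and switch from all treated patients to ITI successes between periods, so the period figures mix change over time with selection on outcome

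*Protocol*

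**What the plan says.** **Objective.** Four of the five secondary objectives are to describe something. The fifth is "To evaluate the impact of ITI treatment with rFVIIIFc on health economics and adherence" (Protocol Synopsis and 6.2; SAP Table 1). Its endpoints are days away from work or school, hospitalization days, adherence and consumption.

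**Analysis sets.** Under Protocol 16.2.2.2, hospitalization days are "summarized descriptively for the ITI Period using the ITIFAS and for the combined Tapering and Follow-Up Periods using the TPFAS", and days away are handled the same way. SAP 4.4.1.2 keeps these sets but moves to a time scale: days away per month and hospitalization days per year. It does so only if n is at least 5; otherwise the data are listed by patient. The ITIFAS is everyone dosed and the TPFAS is everyone who enters tapering (Protocol 16.2.1; SAP section 3). On who can enter, the Synopsis says: "Only subjects who achieve ITI success will enter the Tapering and Follow-Up Periods".

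**Pre-ITI information.** The Screening history in Protocol 13.2 covers bleeding over the previous 12 months, but not earlier missed days or hospital days. Missed days come from the patient diary, whose review starts at Baseline (Protocol 13.4 and Table 1). Hospitalizations are captured as SAEs, which are recorded from consent (Protocol 13.4 and 15).

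**Bleeding.** The set changes here too: the ITI Period uses the ITIFAS, and then "Descriptive statistics for annualized bleeding rate over both Tapering and Follow-Up Periods will also be summarized using the TPFAS".

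**Testing.** "No formal statistical hypothesis testing using inferential statistics will be performed" (Protocol 16).

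**The concern.** An impact needs a reference. The study is single-arm, and for these two endpoints nothing usable is collected from before ITI. What the reader will have is one figure for the ITI Period and one for the time after success, in the same unit, reported under an objective that speaks of impact. The natural step is to compare them.

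The two figures describe different patients. The first includes successes, partial successes, failures and early withdrawals. The second includes successes only, a group picked out by the study's own outcome. If successes and non-successes differ in their underlying rates, the two figures will differ even if every patient's rate is the same throughout. That difference could then be reported as an effect of ITI with rFVIIIFc.

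**Working it through.** The plan states no figure to reproduce: the sample size is set by availability and nothing is tested. The check asks what the two summaries would show if no patient's rate changed at all.

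**Inputs**
- N = 17. Protocol 16.1: "the study plans to prospectively enroll up to 17 subjects who are to receive ITI for the first time". SAP section 2 differs: "the study plans to prospectively enroll up to 30 patients who are to receive ITI for the first time". The result depends on the share of successes, not on N, so this discrepancy does not affect the point.
- s = number of ITI successes, taken as 7, 9 or 12 (41%, 53%, 71%). Protocol 5.1 quotes published success rates of 33% to 88%.
- k = rate in non-successes divided by rate in successes. The documents give no rates, so k is an assumption, shown from 0.5 to 3.

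**SAP time scale.** Set the success rate to 1. The ITI-Period mean on the ITIFAS is (s + (17 − s)k)/17, and the later mean on the TPFAS is 1. The apparent change is 17/(s + (17 − s)k) − 1. For k = 2:
- s = 7: 17/(7 + 20) − 1 = −37%
- s = 9: 17/(9 + 16) − 1 = −32%
- s = 12: 17/(12 + 10) − 1 = −23%

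| Successes | k = 0.5 | k = 1 | k = 1.5 | k = 2 | k = 3 |
|---|---|---|---|---|---|
| 7 | +42% | 0% | −23% | −37% | −54% |
| 9 | +31% | 0% | −19% | −32% | −48% |
| 12 | +17% | 0% | −13% | −23% | −37% |

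With 15 successes (88%), k = 2 gives 17/(15 + 4) − 1 = −11%.

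**Protocol count scale.** The Protocol speaks of numbers of days, so period length matters too. Assume 24 ITI weeks in successes, 48 in non-successes, and 48 weeks (16 + 32) after success. The apparent change is 48 × 17/(24s + 48(17 − s)k) − 1.
- k = 1: 816/648 − 1 = +26% with 7 successes; 816/528 − 1 = +55% with 12.
- k = 2: 816/1128 − 1 = −28% with 7 successes; 816/768 − 1 = +6% with 12.

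On this scale a worsening can appear where rates would show an improvement.

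**Chance variation.** This was checked with 20,000 simulated trials of 17 patients (gamma-Poisson counts, mean one day per 30 days in successes, ITI lengths as above; all assumed). On the time scale at k = 2, the later mean was lower in 91% of runs with 7 successes and 84% with 12. At k = 1 it was lower in about half.

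**Same patients in both periods.** If the ITI-Period figure is restricted to TPFAS patients, the expected change is 0% for every k and s. In the simulation the later mean was then lower in about 48% to 50% of runs at every k, which is chance.

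**The case against.** **No contrast is planned.** The summaries are descriptive, by period, on openly defined sets. Patients without ITI success go to the End of Treatment Visit, so the TPFAS is the only possible set for the later periods. This stands: the plan does not itself make a biased comparison. What remains is that an impact objective invites the comparison and no same-patient figure is committed.

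**The direction is not established.** A reader might infer that an improvement is bound to appear even if no patient changes. The documents do not support that. It needs k above 1. Protocol 5.1 says that "patients with inhibitors are prone to more bleeds", but this concerns bleeding in inhibitor patients generally, not missed or hospital days in failures against successes. Nor do all non-successes keep an inhibitor: one failure criterion in Protocol 7.2.2.2 is a negative titer without either PK parameter, partial successes are negative, and early withdrawals may be. Eventual successes also have inhibitors early in ITI.

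**Pre-treatment data exist.** A reader might infer that there are none. In fact a 12-month bleeding history is collected, and SAP Appendix 2 summarizes bleeds per month before ITI and prior FVIII and bypassing-agent use. The gap is confined to missed days and hospital days. SAE capture from consent adds only the few weeks of Screening for the latter. Bleeding also serves a separate, descriptive objective, and its annualized rate leaves out patients observed for under 90 days.

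**The objective is not empty.** A reader might infer that the trial cannot address it at all. Adherence and consumption have explicit definitions and can be reported as planned.

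**Partial mitigation exists.** Protocol 16.5 and SAP 4.3.5 allow optional subgroup analyses, the latter naming ITI success status, and a patient listing gives outcome and period durations. None of this commits to a paired summary of these endpoints.

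**Conclusion.** The point holds for days away and hospitalization days. No pre-ITI history of either is listed, the analysis set changes from all treated patients to successes, and no same-patient summary is planned. Period and selection on outcome cannot be separated in the two SAP rates.

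On the assumption that non-successes have twice the rate of successes, and that each patient's rate is constant, selection alone produces an apparent fall of 23% to 37% across 12 down to 7 successes. Its size and sign depend on an unknown rate ratio, so it is a risk of misreading and not a demonstrated bias. The annualized bleeding rate has the same change of set, but with pre-ITI history and a descriptive objective it is a lesser matter. This is a secondary objective in a small descriptive study; the change is a cheap improvement.

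**What to change.** 1. In SAP 4.4.1.2, for days away per month and hospitalization days per year, keep the ITIFAS result. Add the ITI-Period result restricted to TPFAS patients and the within-patient difference (rate after success minus ITI-Period rate) on the same time scale. The annualized bleeding rate can optionally be treated the same way.
2. State there that any ITI versus post-ITI statement rests on this column and applies to successes only.
3. In the Protocol Synopsis, Protocol 6.2 and SAP Table 1, change the verb of the objective to *describe*, as in the other four. The paired column removes the change of set but still offers no comparison with the time before ITI.

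The cost is one extra column per table, from data already collected, plus the wording changes. The downside is that the paired column has fewer patients; if there are fewer than 5, the SAP's existing rule would leave individual listings only.

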## Endpoints

The primary endpoint of this study is time to tolerization with a maximum of 12 months (48 weeks) of ITI treatment offered in the study (tolerization defined as inhibitor titer  $<0.6$  BU/mL, rFVIIIFc incremental recovery [IR] of  $\geq 66\%$  of expected, and half-life [ $t_{1/2}$ ] of  $\geq 7$  hours).

The secondary endpoints are as follows:

- ITI success
  - Confirmed negative titers consisting of 2 consecutive negative inhibitor assessments within 2 weeks ( $\pm 3$  days) based on local laboratory results  $<0.6$  BU/mL by the Nijmegen-modified Bethesda assay; determination of negative titer based on the Bethesda assay is acceptable at sites that have not yet adopted the Nijmegen-modified Bethesda assay.
  - IR  $\geq 1.32$  IU/dL per IU/kg in 2 consecutive assessments representing  $\geq 66\%$  of the expected IR 2 IU/dL per IU/kg. ([SmPC](#); [USPI](#))
  - $t_{1/2} \geq 7$  hours.
- Occurrence of relapse (defined as confirmed positive inhibitor titer  $\geq 0.6$  BU/mL), abnormal recovery after tolerance is achieved, and  $t_{1/2} < 7$  hours) during the Tapering or Follow-Up Periods
- Number of bleeding episodes during the ITI Period and during the 48-week (12-month) period after successful ITI performed with rFVIIIFc
- Adverse events and serious adverse events
- Number of days away from work or school
- Number of hospitalization days
- Adherence (defined as percentage of administered doses

CONFIDENTIAL

The information contained herein may not be used, disclosed, or published without the written consent of Bioverativ Therapeutics Inc.

versus planned doses)

- Consumption of rFVIIIFc (measured in total rFVIIIFc use)

The exploratory endpoints are as follows:

[REDACTED]  
[REDACTED]  
[REDACTED]  
[REDACTED]  
[REDACTED]  
[REDACTED]  
[REDACTED]  
[REDACTED]

The exploratory endpoint [REDACTED]  
[REDACTED] will be reported outside the clinical  
study report.

Study Design:

An open-label, single-arm, interventional, multicenter study designed to explore the use of rFVIIIFc for ITI in subjects with severe hemophilia A, who are undergoing ITI treatment for the first time.

The study consists of 1) a 4-week (1-month) Screening Period; 2) a maximum of a 48-week (12-month) ITI Period; 3) a minimum of a 16-week (4-month) Tapering Period after all criteria for tolerization have been met; and 4) a 32-week (8-month) Follow-Up Period. Only subjects who achieve ITI success will enter the Tapering and Follow-Up Periods. During the Tapering and Follow-Up Periods, the subject's dose will be adjusted to achieve the prophylactic dose.

Study Location and Number of Sites:

Approximately 30 sites in the USA, Europe, Japan, and Canada

Number of Planned Subjects:

Up to 17 subjects

Study Population:

This study will be conducted in male subjects of any age with severe hemophilia A and high-titer inhibitors (historical peak  $\geq 5$  BU/mL), who have been previously treated with any plasma-derived FVIII or recombinant conventional or EHL FVIII and are undergoing ITI treatment for the first time.

CONFIDENTIAL

The information contained herein may not be used, disclosed, or published without the written consent of Bioverativ Therapeutics Inc.

Page 17

VV-CLIN-0542000 3.0

Detailed criteria are described in Section 8.

Treatment Groups: This is a single-arm study that will enroll up to 17 subjects

Duration of Treatment and Follow-Up: Study duration for each subject will vary based on time to ITI success. The maximum individual subject study duration is expected to be approximately 2 years.

CONFIDENTIAL

The information contained herein may not be used, disclosed, or published without the written consent of Bioverativ Therapeutics Inc.

[figure not shown]
Page 18

VV-CLIN-0542000 3.0

